2.4.3 Prohibited treatment

Analysis of concomitant medications, procedures that are prohibited as per protocol (see protocol Section 5.5.8) and given during the conduct of the study will be addressed by the currently planned outputs for the protocol deviations.

No separate outputs will be produced related specifically to prohibited medications.

2.5 Analysis of the primary objective

2.5.1 Primary endpoint

The primary efficacy variable is the change from baseline in monthly migraine days in the last 4 weeks of the 12-week treatment period.

Analysis of the primary endpoint will utilize the FAS. Subjects will be analyzed according to their randomized treatment group regardless of the actual treatment received during the study.

2.5.2 Statistical hypothesis, model, and method of analysis

The primary endpoint of the study will be tested for erenumab 70 mg compared to placebo.

Null hypothesis: There is no difference between erenumab 70 mg group and placebo group, in terms of change from baseline in monthly migraine days in the last 4 weeks of the 12-week treatment period.

Alternative hypothesis: There is a difference between erenumab 70 mg group and placebo group, in terms of change from baseline in monthly migraine days in the last 4 weeks of the 12-week treatment period.

The null hypothesis will be rejected if the observed p-value for the between-group comparison is less than the significant level adjusted according to the alpha spending function with the

O'Brien-Flemming approach. The nominal p-value threshold will be calculated upon the exact information collected in the interim analysis, considering the alpha-level spent at interim analysis and considering the actual correlation among the test statistics, in order to achieve a cumulative type I error smaller than the desired significance level (i.e. smaller than the 5% for a two-sided test).

The primary efficacy endpoint variable will be analyzed using a linear mixed effects repeated measures model based on observed monthly data during treatment period, with treatment, scheduled visit, treatment by visit interaction, and the stratification factors and baseline values as covariates. If applicable, unstructured covariance structure is assumed. Least squares means (LSMs) for treatment groups and its associated 95% confidence intervals, difference of LSMs compared to placebo group and the associated 95% confidence interval of the difference, as well as the nominal two-sided p-values, will be tabulated by visit and treatment.

2.5.3 Handling of missing values/censoring/discontinuations

For the primary analysis, missing data will not be imputed.

2.5.4 Sensitivity analyses

Multiple imputation (MI) techniques applying missing at random (MAR) and missing not at random (MNAR) approaches will be used to assess the impact of missing values on the interpretation of the results during study. In addition, the baseline observations carried forward (BOCF) method will also be used. After imputation, the primary efficacy variable at week 12 will be analyzed using an analysis of covariance (ANCOVA) model including treatment group and stratification factor as fixed effects in the model with baseline value as covariate.

2.6 Analysis of secondary efficacy objective(s)

2.6.1 Secondary endpoints

The secondary efficacy variables are:

- Change from baseline in migraine-related disability and productivity as measured by the mMIDAS during the last 4 weeks of the 12-week treatment period
- Proportion of subjects who achieve at least a 50% reduction from baseline in monthly migraine days in the last 4 weeks of the 12-week treatment period
- Change from baseline in monthly acute headache medication days during the last 4 weeks of the 12-week treatment period

2.6.2 Statistical hypothesis, model, and method of analysis

Analysis of secondary efficacy endpoints will utilize the FAS. Subjects will be analyzed according to their randomized treatment group regardless of the actual treatment received during the study.

The above continuous change from baseline efficacy endpoints will be analyzed using a linear mixed effects repeated measures model similar to the primary efficacy variable.

The dichotomous endpoint (Proportion of subjects who achieve at least a 50% reduction from baseline in monthly migraine days in the last 4 weeks of the 12-week treatment period) will be analyzed based on Cochran-Mantel-Haenszel (CMH) test after subjects who have missing monthly migraine day data at the last 4 weeks imputed as non-responders.

The description of the models can be found in [Section 5.4](#)

In all cases, estimates (difference or odds ratio) of treatment group compared to placebo group with associated nominal 95% confidence intervals and nominal two-sided p-values will be provided.

2.6.3 Handling of missing values/censoring/discontinuations

For the proportion of subjects who achieve at least a 50% reduction from baseline in monthly migraine days in the last 4 weeks of the 12-week treatment period, the missing data will be imputed as non-responder (NRI).

2.6.4 Sensitivity analyses

In order to assess the robustness of the analysis for the secondary endpoint “Proportion of subjects who achieve at least a 50% reduction from baseline in monthly migraine days in the last 4 weeks of 12-week treatment period”, a logistic regression analysis that includes treatment and stratification factors as fixed effects and baseline migraine days as covariate, will be used to get odds ratio of AMG 334 group vs placebo in the 50% response rate after the missing data are imputed as non-response.

The odds ratio of each treatment group compared to placebo group with associated 95% confidence intervals and p-values will be provided.

2.7 Safety analyses

For safety endpoints in DB period, all randomized subjects who received at least one dose of investigational product (i.e., utilizing the SAF) will be analyzed based on the actual treatment received (defined as the randomized treatment unless a subject has received the incorrect dose the entire treatment period).

No statistical testing comparing treatment groups will be performed in the safety analyses.

Missing data will not be imputed for safety endpoints.

The safety analysis for DB period [REDACTED] will be displayed separately and pertinent to all safety endpoints below, unless other specified.

2.7.1 Adverse events (AEs)

The Medical Dictionary for Regulatory Activities (MedDRA) version 21.0 or later will be used to code all adverse events (AE) to a system organ class (SOC) and a preferred term (PT). All adverse events will be graded using the Common Terminology Criteria for Adverse Events (CTCAE) Version 4 or higher. All adverse event tables will be summarized by treatment group.

The overall subject incidence of AEs and exposure-adjusted subject incidence will be summarized for all TEAEs, AEs leading to discontinuation of study treatment, all treatment-related AEs, SAEs, SAEs leading to discontinuation of study treatment, treatment-related SAEs and deaths as defined in **Table 2-4**.

Table 2-4 AE Summaries of subject incidence and exposure-adjusted subject incidence

Category	Summary by SOC and PT	Summary by SOC, PT and maximum CTCAE grade	Summary by PT only
All TEAEs	Y	Y	Y
SAEs	Y	Y	Y
AEs leading to discontinuation of study treatment	Y		
All treatment-related AEs	Y		
SAEs leading to discontinuation of study treatment	Y		
Treatment-related SAEs	Y		
Deaths	Y		

For all AEs tables presented by SOC and PT (and grade), the SOCs will be presented in alphabetical order and PTs will be ordered within the SOC by decreasing order of frequency.

AE tables by preferred term only will be sorted in descending order of frequency.

Note, for exposure-adjusted AEs the sorting will be based on the exposure-adjusted subject incidence rate.

Subject incidence all treatment-related AEs and serious treatment-related AEs will be tabulated by SOC and PT for the DB period.

All AEs, deaths (see [Section 2.7.2](#) for details), SAEs and AEs leading to permanent study drug discontinuation will be listed separately.

2.7.1.1 Adverse events of special interest / grouping of AEs

Not applicable.

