Apart from the global clinical program focused on Caucasian population, a Phase 1 study in Japanese subjects (Study 20120130) and a Phase 2 study (Study 20120309) in Japanese subjects with EM were conducted to support the registration in Japan. The PK of erenumab at 70 mg was similar and there is no ethnic difference between healthy Japanese and Caucasian subjects. Study 20120309 is a Phase 2, multicenter, randomized, double-blind, placebo-controlled, parallel-group study. A total of 475 subjects were randomized 2:1:2:2 to receive placebo, erenumab 28 mg, 70 mg, or 140 mg during the 24-week double-blind treatment phase. While the results were significant for all 3 doses evaluated, the efficacy on the primary and secondary endpoints for the 28 mg dose were almost 50% lesser in magnitude than the 70 mg dose. Comparable efficacy was seen between 70 mg and 140 mg doses. Besides, the safety profile was similar to placebo and also comparable between Japanese and Caucasian subjects. A multi-regional, three arms (placebo, 70 mg and 140 mg groups), double-blinded, Phase 3 study (Study CAMG334A2302) in the EM population, primarily in Asia is currently ongoing. The purpose of this study is to obtain data from regions not adequately represented in the global pivotal trials, and to support registration in countries or regions requiring local data for regulatory approval (India, Korea, and Taiwan).

The safety and tolerability profile of erenumab was similar to placebo in both treatment groups for all studies. No adverse event (AE) occurred with an incidence of > 6%; the most commonly reported adverse events included injection site pain, infection of the upper respiratory tract and nausea. Based on a pooled analysis across four placebo-controlled trials, the identified adverse drug reactions include injection site reactions, constipation, muscle spasm and pruritus.

In view of limited information on ethnic subgroups, especially Chinese, this trial will provide additional information about erenumab safety and efficacy in CM in a mainly Chinese population and provide local data for regulatory submission.

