#### 4.5 Risks and benefits

Key risks and benefits are briefly summarized below. For further information, please refer to the current Investigator Brochure (IB).

The safety of erenumab in migraine prophylaxis was assessed from integrated safety analyses of 4817 subjects with migraine who received at least one dose of erenumab (dose level at 7, 21, 70, or 140 mg), representing 4418.3 subject-years of exposure as of data cut-off date 16 May 2019 as per Investigator's Brochure edition 11.1. Overall, the safety and tolerability profile of erenumab was similar between the 140 mg and 70 mg doses and also comparable to placebo. For adverse drug reactions refer to Section 7 (Summary and Data and Guidance for the Investigator) of the IB.

Overall, to date, there is no evidence from nonclinical and clinical data of risk of cardiovascular effects. On the theoretical basis of the mechanism of action of erenumab, CGRP receptor blockade may reduce compensatory vasodilation, particularly under ischemic conditions. To determine the potential impact of erenumab on total exercise time, time to exercise-induced angina, and ST depression during a Treadmill Test in subjects with stable angina, a double-blind, placebo-controlled study conducted and demonstrated that erenumab does not impact exercise tolerance or interfere with homeostatic vasodilatory mechanisms in subjects with chronic myocardial ischemia. However, in this planned study, cardiovascular effects continue to be monitored, and subjects with major cardiovascular disease within 12 months prior to screening will be excluded from participation.

All biologicals, including fully human proteins, have the potential to induce immunogenicity leading to the development of specific anti-drug antibodies. Overall, erenumab treatment is associated with a low incidence of immunogenicity. While the number of anti-AMG 334 antibody-positive subjects is limited, impact analyses suggest that despite a modest reduction in exposure among anti-AMG 334 antibody-positive subjects, there was no impact of anti-AMG 334 antibody development on efficacy or safety. Subjects in clinical studies will continue to be monitored for the development of anti-erenumab antibodies and associated clinical sequelae.

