### **Adverse events**

The Medical Dictionary for Regulatory Activities will be used to code all adverse events (AEs). A treatment-emergent adverse events (TEAE) is defined as any adverse event that develops after initiation of study treatment until the end of the last study visit or any event already present that worsens following exposure to the study treatment until the end of the last study visit. Subject incidence rates of TEAEs will be tabulated by SOC and PT by treatment group, separately for the double-blind period [REDACTED]. Tables of TEAE by maximum toxicity grade, fatal AEs, serious AEs, AEs leading to withdrawal from investigational drug, treatment-related AEs, and serious treatment-related AEs will also be presented in a similar format as TEAE. Additionally, a listing of subject with TEAE will be presented. The TEAEs identified as potential risk will be summarized separately.

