2.1.4.2 Safety endpoints

Subject Incidence

The subject incidence for a given event in a given period is defined as the number of subjects with at least one reported occurrence of the event divided by the number of subjects who entered that period. For subjects with multiple occurrences of the same event, the event will only be counted once per subject.

Exposure-Adjusted Subject Incidence Rate

The exposure-adjusted subject incidence rate for a given event in a given period is defined as the number of subjects with at least one reported occurrence of the event in a given time period divided by total subject years at risk in that period. The time at risk for each subject will differ for each adverse event. For subjects with events, only the time until the first event contributes to the total subject years at risk. For subjects who do not experience the event, the time at risk will be up to the last available visit. This rate will be presented per 100 subject years. For subjects with multiple occurrences of the same event, the event will be only counted once per subject.

Treatment-Emergent Adverse Event (TEAE)

Adverse Events (AEs) recorded on the Adverse Events eCRF page that occurs on or after first dose of investigational product and up to and including end of study.

Serious Adverse Event (SAE)

SAEs determined by the flag indicating if the adverse event is serious on the Adverse Events eCRF page will include those that occur after signing of the informed consent and up to and including end of study.

Treatment-Emergent Serious Adverse Event

A treatment-emergent serious adverse event is an SAE considered to be treatment-emergent.

Treatment-Related Adverse Event

A treatment-related AE is defined as a treatment-emergent adverse event that is considered by investigators to have reasonable possibility that it may have been caused by IP as determined by the flag indicating that there is a reasonable possibility that the AE is related to investigational product on the Adverse Events eCRF page.

Treatment-Related Serious Adverse Event

A treatment-related serious adverse event is an SAE considered to be treatment-related.

Adverse Event leading to discontinuation of study treatment

An AE leading to discontinuation of study treatment will be identified by the item “Action Taken With Study Treatment” on AE page of CRF when it’s reported as “Drug withdrawn”.

Serious Adverse Event leading to discontinuation of study treatment

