 - Change from baseline in migraine-related disability and productivity as measured by modified MIDAS during the last 4 weeks of the 12-week treatment period (as defined in [Section 2.6](#))
 - Adverse events (as defined in [Section 2.7.1](#))

3 Sample size calculation

The planned total sample size in this proposed China-centric phase 3 study is 550 subjects. The key assumptions in calculating the sample size are based on prior results from erenumab global pivotal study. A treatment difference in terms of change from baseline on MMDs during Week 9-12 (primary endpoint) for erenumab 70 mg vs. placebo is assumed at -2.0 days. The common standard deviation of the primary variable is assumed at 6.8. Given a 1:1 randomization ratio among erenumab 70 mg and placebo, it requires a total of 550 subjects (including 10% drop out rate) to achieve approximate 90% power to demonstrate the treatment difference of erenumab 70 mg compared with placebo under two-sided 0.05 alpha level. The impact of spending alpha at unblinded interim analysis on sample size and power is relatively negligible. Having this interim analysis with alpha spending at 0.014 two-sided, at final analysis an observed p-value ≤ 0.046 two-sided would be required (given that the interim analysis was performed when 70% subject finished treatment or early withdraw). With that said, the overall power will be maintained at approximately 88% with planned sample size.

The sample size for Chinese sub-population will make sure the consistency of treatment effect between Chinese and total population. The methods for consistency assessment are proposed as,

$\Pr(D_{\text{China}} / D_{\text{overall}} > 0.5) > 95\%$,

which means that this China study should have high probability ($>95\%$) to demonstrate consistency where the treatment effect (treatment difference of erenumab compared with placebo) observed in the Chinese population should be as high as at least 50% of the treatment effect observed in the overall study population in the prospective trial, assuming there is no difference between the Chinese population assessed in the trial and the overall population.

To meet the above criteria, approximately 350 (out of 550 for the overall study) Chinese subjects will be recruited.

At the interim analysis, as long as China population takes the majority of the overall population, there should have high likelihood to demonstrate the consistency as well.

4 Change to protocol specified analyses

Not applicable.

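### The protocol promises a separate summary of potential-risk adverse events; the SAP marks that analysis as not applicable, leaves it out of its AE table and declares no change

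*SAP*

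**What the plan says.** Protocol 12.5.2, under adverse events, sets out the planned AE tables and then adds: "The TEAEs identified as potential risk will be summarized separately". It does not say which events these are.

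Two other protocol sections bear on what they could be. Section 4.5 describes a theoretical ischaemic mechanism for CGRP receptor blockade, reports no evidence of cardiovascular harm to date, and says that in this study "cardiovascular effects continue to be monitored". Section 1.1 states that "the identified adverse drug reactions include injection site reactions, constipation, muscle spasm and pruritus", based on a pooled analysis of four placebo-controlled trials.

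In the SAP, the section headed "Adverse events of special interest / grouping of AEs" (2.7.1.1) is answered as not applicable. The AE tables are fixed in SAP 2.7.1 by "Table 2-4 AE Summaries of subject incidence and exposure-adjusted subject incidence", which has no row for potential-risk events. The section headed "4 Change to protocol specified analyses" is also answered as not applicable. The only AE grouping visible in the SAP is in 2.7.4.2, where post-baseline hypertension or worsening hypertension is identified from AEs by a narrow SMQ list and subjects are counted. The interim AE analysis in SAP 2.12.2 is defined by reference to 2.7.1.

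**The concern.** A reader who takes the protocol at its word expects a table showing, for each potential risk, how many subjects per arm had at least one event. The SAP is where the risks should be named and their search terms fixed. Instead it closes the relevant section, and because Section 4 declares no change, nothing shows whether this was a decision or an oversight.

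Two things are at stake. First, for a risk made up of several preferred terms, the planned tables give no incidence per subject. Second, if someone later asks for a grouped count, the terms would be chosen after the data are known, and the choice could be shaped by the result. Both matter in a trial meant to supply data in a mainly Chinese population, on which the protocol says information is limited.

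**Working it through.** The plan states no figure for this point, so the check is a comparison of texts plus one counting argument.

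**Step 1: match the protocol's AE tables to SAP 2.7.1.**

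| Protocol 12.5.2 | SAP 2.7.1, Table 2-4 |
|---|---|
| TEAEs by SOC and PT | present |
| TEAEs by maximum grade | present, as a column |
| Fatal AEs | present, as deaths |
| Serious AEs | present |
| AEs leading to withdrawal from study drug | present |
| Treatment-related AEs | present |
| Serious treatment-related AEs | present |
| Potential-risk TEAEs, separately | absent |

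Seven of the eight are carried over. The eighth is not, and the section where it would be defined is marked as not applicable. That entry is legible text, not a redaction.

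**Step 2: see whether it is declared.** SAP Section 1 says the SAP will set out planned deviations from the protocol. SAP Section 4 reports none. The omission is therefore undeclared.

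**Step 3: see whether another section supplies it.** SAP 2.7.4.2 gives a pooled subject count for hypertension. SAP 2.7.3 (liver enzymes) and 2.7.4.1 (ECG) summarise measurements and do not group AEs. No other pooled AE count is visible.

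**Step 4: see whether it can be recovered from the planned tables.** SAP 2.1.4.2 defines subject incidence so that: "For subjects with multiple occurrences of the same event, the event will only be counted once per subject". That removes repeats within one event term. It does not remove overlap between terms, because one subject can appear in several PT rows. If the PT rows for one risk hold n1, ..., nk subjects, the number with any of them lies between max(n1, ..., nk) and n1 + ... + nk, subject to the arm size.

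With assumed rows of 3, 2, 2 and 1 subjects, chosen only to show the logic:
- lower bound: max = 3
- upper bound: 3 + 2 + 2 + 1 = 8

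The same holds for exposure-adjusted incidence. SAP 2.1.4.2 counts time at risk only to the first event and separately for each event, so a grouped rate needs its own denominator. A SOC row would serve as the grouped count only if the risk's terms filled that SOC and nothing else did. The documents do not give MedDRA placement, so this cannot be assumed either way.

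**Step 5: trace the interim.** SAP 2.12.2 takes its AE analysis from 2.7.1, both overall and for the Chinese sub-population. The SAP's interim package therefore has the same omission, and an edit to 2.7.1 would correct both.

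**The case against.** The case on the other side has several parts.

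- **The events are counted.** Every TEAE and SAE is tabulated by SOC and PT, by maximum grade and by PT alone, with exposure-adjusted incidence, and all AEs and SAEs are listed. This stands. A reader might infer that the named risks go uncounted, and that is wrong. Only the pooled count per risk is missing.
- **The protocol never lists the potential risks.** This also stands. The four events in protocol 1.1 are called identified reactions, so the documents do not show that injection site reactions, for example, were promised a separate table. Cardiovascular effects fit best, but that too is an inference, and monitoring is not the same as a promise of a pooled AE table. The hypertension summary might be part of what was meant, although the SAP does not say so. None of this removes the mismatch: an undefined promise is a reason to define it.
- **Serious vascular events would probably sit together in the SAE listing.** Often true, and the coded subject-level data exist, so a count could be made by hand. It would be an unplanned count with terms chosen late. Exclusion criterion 17 groups several vascular diagnoses, but as a history screen; it does not define an AE composite.
- **The effect on the DMC is not shown.** This stands. One might infer that the stop-or-continue recommendation is compromised. The protocol gives the DMC regular unblinded safety reviews and leaves the details to a charter. Neither the charter nor the table shells are available, so what the DMC would lack is unknown.
- **No loss of signal can be quantified.** Also accepted. Any figure for how far splitting over PT rows dilutes an imbalance would need event rates and a MedDRA split that the documents do not give, and SAP 2.7 plans no safety testing.

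**Conclusion.** The point holds as a documented mismatch: the protocol commits to a separate summary of potential-risk TEAEs, and the SAP marks it as not applicable, omits it from Table 2-4 and declares no change. Its size is one descriptive safety analysis out of the eight AE tabulations in protocol 12.5.2. The consequence is that, apart from hypertension, no pooled subject count is defined for any risk, including the cardiovascular and ischaemic effects discussed in protocol 4.5.

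The primary analysis, type I error, power and data collection are not affected. The documents support no claim that risks go uncounted, that a given imbalance would be missed, or that the DMC decision would be impaired.

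The conclusion assumes that the redacted parts of the SAP and the unavailable table shells do not contain the summary. If a shell did, it would contradict SAP 2.7.1.1 and the SAP would still need correcting.

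**What to change.** Before unblinding:

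1. Replace the entry in SAP 2.7.1.1 with a list of the potential-risk TEAEs and the search terms for each. Include at least cardiovascular/ischaemic events, with a cross-reference to the hypertension SMQ already in 2.7.4.2. The identified reactions in protocol 1.1, such as injection site reactions, are a reasonable addition, but the protocol does not clearly require them.
2. Add a row to Table 2-4 giving subject incidence and exposure-adjusted incidence by arm for each group, counting each subject once per group.
3. Confirm in SAP 2.12.2 that the row is part of the interim AE package.

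If the sponsor intends to drop the summary, record that and the reason in SAP Section 4 instead.

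The cost is SAP wording and one table shell on coded data already collected. The table adds a few descriptive rows, with no testing and no use of alpha.
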